3.0 Patient Eligibility

3.1 Inclusion Criteria

3.11 Age \geq 18 years

3.12 Histological confirmation of non-clear cell renal cancer (including Chromophilic (papillary), Chromophobic, Oncocytic, sarcomatoid, Collecting duct (Bellini's duct), translocation-type carcinoma or medullary renal cell carcinoma.

3.13 Up to one prior treatment for metastatic non clear cell carcinoma is allowed prior to registration as long as the agent used to treat was not pazopanib.

3.14 Measurable or non-measurable metastatic disease as defined in Section 11.0.

3.15 ECOG Performance Status (PS) 0, 1 or 2 (Appendix II).

3.16 The following laboratory values obtained \leq 14 days prior to registration.

- ANC \geq 1500
- PLT \geq 100,000
- HgB $>$ 9.0 g/dL. NOTE: Subjects may not have had a transfusion within 7 days of registration.)
- Total Bilirubin $<$ 1.5 x ULN
- Alanine amino transferase (ALT) \leq 2.5 X ULN. NOTE: Concomitant elevations in bilirubin and ALT above 1.0 x ULN (upper limit of normal) is not permitted.

- Aspartate aminotransferase (AST) $\leq 2.5 \times$ ULN. Note: Concomitant elevations in bilirubin and AST above $1.0 \times$ ULN (upper limit of normal) is not permitted.
- Urine Protein to Creatinine Ratio (UPC; appropriate appendix) (UPC) < 1
NOTE: If UPC ≥ 1 , then a 24-hour urine protein must be assessed. Subjects must have a 24-hour urine protein value < 1 g to be eligible.
- Prothrombin time (PT) or international normalized ratio (INR) $\leq 1.2 \times$ ULN NOTE: Subjects receiving anticoagulant therapy are eligible if their INR is stable and within the recommended range for the desired level of anticoagulation

3.17 A female is eligible to enter and participate in this study if she is of:

a. Non-childbearing potential (i.e., physiologically incapable of becoming pregnant), including any female who has had:

- A hysterectomy
- A bilateral oophorectomy (ovariectomy)
- A bilateral tubal ligation
- Is post-menopausal

Subjects not using hormone replacement therapy (HRT) must have experienced total cessation of menses for ≥ 1 year and be greater than 45 years in age, OR, in questionable cases, have a follicle stimulating hormone (FSH) value > 40 mIU/mL and an estradiol value < 40 pg/mL (< 140 pmol/L).

Subjects using HRT must have experienced total cessation of menses for ≥ 1 year and be greater than 45 years of age OR have had documented evidence of menopause based on FSH and estradiol concentrations prior to initiation of HRT

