CT scan of chest, abdomen or pelvis, MRI, etc		X ^R			X ⁷	
Bone Scan					X ⁵	
EKG		X ^R	X			
Medication Diary			X ³			

1. SGOT, SGPT, total bili, Na, K, Cl, CO₂, BUN, creatinine, LDH, hemoglobin, calcium, albumin, total protein, magnesium, phosphorus and alkaline phosphatase.
2. For women of childbearing potential, ≤7 days prior to registration.
3. The diary must begin the day the patient starts taking the medication and must be completed per protocol and returned to the treating institution OR compliance must be documented in the medical record by any member of the care team.
4. +/- 3 days
5. If applicable
6. Research funded, cycles 1 and 2 only
7. Use the same method throughout the study. Follow-up scans to be performed every other cycle (8 weeks). Repeat measurements are required 8 weeks following an objective Response. See Section 11.0 for full RECIST criteria.
8. Every 4 months while on study, sooner should clinical symptoms indicate. These follow-up echocardiograms will coincide with restaging visits.
9. SGOT, SGPT, total bili, only and can be done at study site or locally and faxed.
- R Research funded (see Section 19.0)

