- 6.4 At the time of registration, the following will be recorded:
- Patient has/has not given permission to store and use his/her sample(s) for unspecified future research of renal cancer at Mayo.
 - Patient has/has not given permission to store and use his/her sample(s) for future

- research to learn, prevent, or treat other health problems.
- Patient has/has not given permission for MCCC to give his/her sample(s) to researchers at other institutions.
- Patient has given permission to store and use his/her samples for the mandatory future banking(section 14.1)

- 6.5 Treatment cannot begin prior to registration and must begin \leq 14 days after registration.
- 6.6 Pretreatment tests/procedures (see Section 4.0) must be completed within the guidelines specified on the test schedule.
- 6.7 All required baseline symptoms (see Section 10.3) must be documented and graded.
- 6.8 Treatment on this protocol must commence at Mayo Clinic Rochester, Mayo Clinic Arizona, or Mayo Clinic Florida under the supervision of a medical oncologist who confirms the patient is a suitable candidate for this study.
- 6.9a Study drug is available on site.

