7.12 Dosage and Administration

Administration of pazopanib with a high-fat or low-fat meal results in an approximately 2-fold increase in area under the plasma drug concentration curve (AUC) and maximum observed plasma drug concentration (C_{max}).

Pazopanib should be taken orally without food at least one hour before or two hours after a meal. The tablets should be swallowed whole and must not be crushed or broken. The time of day the tablets are taken should be relatively constant.

If a dose is missed, the subject should take the dose as soon as possible, but only if there are 12 or more hours remaining before the next dose is due. If the next dose is due in less than 12 hours, the subject should skip the missed dose and take the next dose as scheduled.

If vomiting occurs after taking pazopanib, the subject should not take a replacement dose on that day. The subject should resume taking pazopanib at the next scheduled dose on the following day. If vomiting persists, the subject should be instructed to notify the investigator.

As a general rule, if dose reduction of pazopanib is necessary, the dose should be reduced stepwise by 200 mg at each step, and the subject should be monitored for approximately 10 to 14 days at each dose level. If toxicity does not abate during this monitoring time, the medication may need to be interrupted and/or the dose further decreased with continued monitoring for an additional 10-14 days at each dose level, and so on.

If the toxicity has abated with reduction of the dose and dose re-escalation is considered safe by the investigator, the dose can then be increased step-wise back to the pre-event dose (in 200 mg increments, after monitoring for 10-14 days at each dose level to ensure that toxicity did not recur or worsen).

If a subject's treatment has been interrupted for more than 21 days, the Investigator must contact the Study Physician to review the subject's condition in order to resume the treatment.

- 7.2 Patients can be instructed in administration techniques and granted treatment independence with nursing staff approval.
- 7.3 For this protocol, the patient must return to Mayo Rochester, Florida, or Arizona for evaluation at least every 28 days (+/- 3 days).

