Asymptomatic: Absolute decrease of >10% in LVEF compared to baseline and ejection fraction below the institution's LLN OR LVEF drop >15% from baseline regardless of whether value is below institution's LLN.	
 • Interrupt pazopanib study treatment and repeat ECHO within 2 weeks^b and monitor and control BP. • If the LVEF recovers within 4 weeks (defined as LVEF \geqLLN and absolute decrease \leq10% compared to baseline) 
 ○ Restart study treatment^f reduced by one dose level (Please consult with Novartis if there are any questions prior to restarting) ○ Repeat ECHO 2, 4, 8 and 12 weeks after re-start; monitor BP; continue in intervals of 12 weeks thereafter • If repeat LVEF does not recover within 4 weeks 
 ○ Consult with cardiologist ○ Permanently discontinue pazopanib treatment Repeat ECHO after 2, 4, 8, 12, and 16 weeks or until resolution 
Please Consult with Novartis if there are any questions

Symptomatic ^c : Grade 3: resting LVEF 39-20% or >20% absolute reduction from baseline	
 • Permanently discontinue pazopanib treatment • Consult with cardiologist • Repeat ECHO after 2, 4, 8, 12, and 16 weeks or until resolution
Symptomatic ^c : Grade 4: resting LVEF <20%	
Prolongation of QTc Interval: If the QTc is prolonged, the ECG should be manually read to ensure accuracy of the reading. The values below refer to manually-read ECGs. REFER READER TO ECG SECTION IN PROTOCOL	
QTc \geq 480 < 500 msec	Continue pazopanib; monitor as clinically indicated.
QTc \geq 500 msec	Discontinue pazopanib and continue follow-up per protocol.
Proteinuria	
UPC <3	Continue pazopanib at the current dose; monitor as clinically indicated
UPC \geq 3 or 24-h urine protein \geq 3g	
Step 1. Interrupt pazopanib.
 
Step 2. Weekly UPC or 24-hr urine protein monitoring until UPC is <3 or 24-hr urine protein is <3 grams. Then restart pazopanib dose-reduced by 200 mg.
 
Step 3. If UPC \geq3 or 24-h urine protein \geq3g recurs, repeat steps 1 and 2.
 
Step 4. If UPC \geq3 or 24-hr urine protein \geq3 recurs and the pazopanib dose can no longer be reduced, discontinue pazopanib and continue follow-up per protocol.

Hemorrhage /Bleeding: Investigate and document underlying etiology of the bleeding	

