Grade 1	For hemoptysis, interrupt pazopanib and contact the Novartis Study Physician to discuss whether further treatment with pazopanib is appropriate. For other Grade I hemorrhage/bleeding events, continue pazopanib at the current dose; monitor as clinically indicated.
Grade 2	Step 1. If pulmonary or GI bleed (other than hemorrhoidal bleeding), discontinue pazopanib and continue follow-up per protocol. Otherwise, interrupt pazopanib until the AE resolved to \leq Grade 1. Step 2. Restart pazopanib ; consider reducing dose and monitor as clinically indicated.
Grade 3 or 4, or Recurrent \geq Grade 2 event after dose interruption/reduction.	Discontinue pazopanib and continue with follow-up per protocol.
Venous Thrombosis (DVT, PE)	
Grade 2	Continue pazopanib at the current dose; monitor as clinically indicated
Grade 3	Step 1. Interrupt pazopanib . Step 2. Initiate and monitor anticoagulation as clinically indicated. Step 3. Resume pazopanib at reduced dose only if all of the following criteria are met: 
 • The subject must have been treated with anticoagulant at the desired level of anticoagulation for at least one week. • No Grade 3 or 4 or clinically significant Grade 2, hemorrhagic events have occurred while on anticoagulation treatment. Subject should be monitored as clinically indicated during anticoagulation treatment and after resuming study treatment. When treating with warfarin, international normalized ratio (INR) should be monitored within three to five days after any change in pazopanib dosing (eg, re-initiating, escalating/de-escalating, or discontinuing pazopanib), and then at least weekly until the INR is stable. The dose of warfarin (or its derivatives) may need to be adjusted to maintain the desired level of anticoagulation
Grade 4 and/or PE	Discontinue pazopanib and continue follow-up per protocol.
Arterial Thrombosis/Ischemia	
Any Grade	Discontinue pazopanib and continue follow-up per protocol.
Thrombocytopenia: Investigate and document underlying cause	
Grade 1 or 2	Continue pazopanib with current dose; monitor as clinically indicated.
Grade 3 or 4	Step 1. Interrupt pazopanib until toxicity resolves to \leq Grade 2.

	Step 2. Restart pazopanib dose-reduced by 200 mg and monitor as clinically indicated. If no recovery to \leq Grade 2 or recurrent Grade 3 or 4 thrombocytopenia, discontinue IP and follow-up per protocol.

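### Section 8.3 stops pazopanib for heavy proteinuria, but no urine protein test is scheduled after registration to detect it

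*Combined protocol and SAP*

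**What the plan says.** The proteinuria rule is in Section 8.3 and has two rows.

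- Below UPC 3: "Continue pazopanib at the current dose; monitor as clinically indicated".
- At UPC 3 or more, or 24-hour urine protein of 3 g or more, four steps apply. The drug is interrupted. Then comes "Step 2. Weekly UPC or 24-hr urine protein monitoring until UPC is <3 or 24-hr urine protein is <3 grams", followed by a restart 200 mg lower. The sequence repeats on recurrence. If it recurs and the dose cannot be lowered further, treatment ends.

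In the Section 4.0 test schedule the UPC row carries one mark, in the column for the 14 days before registration. The columns for Day 1 of each cycle, weeks 2, 6 and 10, every other cycle and end of treatment are blank, and no footnote adds a test. There is no row for 24-hour urine protein or urinalysis.

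The baseline test serves eligibility. Section 3.16 asks for UPC below 1. If it is 1 or higher, "then a 24-hour urine protein must be assessed. Subjects must have a 24-hour urine protein value < 1 g to be eligible", with no upper limit on the spot UPC itself. Section 7.4 allows up to 12 months of therapy.

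**The concern.** A mandatory dose rule needs a measurement that can set it off. Here the rule requires interruption, reduction and finally discontinuation, but the schedule never produces the value it depends on. Weekly testing does not fill the gap, because it starts after a high value has been found and ends once the value is back below 3. First detection is therefore unscheduled, and so is detection of a recurrence after restart.

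Heavy protein loss often causes no symptoms. A fully compliant site could continue dosing a patient whose urine protein is above the level at which the protocol requires a stop. The proteinuria rate in the toxicity profile (Goal 2.23) would also rest on whoever happened to be tested.

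**Working it through.** There is no stated figure to reproduce. The check compares the rule with the schedule and then sizes the gap.

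**Step 1. Other thresholds in Sections 8.3 and 8.4 against Section 4.0**

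| Threshold | Scheduled on-treatment measurement |
|---|---|
| Blood pressure | Vital signs, Day 1 of every cycle |
| LVEF | Echocardiogram, every 4 months |
| QTc | EKG, Day 1 of every cycle |
| Platelets | CBC, Day 1 of every cycle |
| ALT and bilirubin | Chemistries, Day 1 of every cycle, plus weeks 2, 6 and 10 |
| UPC or 24-hour urine protein | None |

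Section 8.3 uses similar discretionary wording for QTc of 480 to below 500 msec ("Continue pazopanib; monitor as clinically indicated") and for Grade 1 or 2 platelets ("Continue pazopanib with current dose; monitor as clinically indicated"). In both cases that discretion is added to a test done every cycle. For urine protein nothing lies underneath it.

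**Step 2. Search for a urine protein test elsewhere**

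- The scheduled chemistries (Section 4.0, footnote 1) include albumin and total protein, but these are serum tests.
- Section 10.6 does not list proteinuria among events graded at each evaluation. Section 10.61 captures related Grade 2 events and all Grade 3 and 4 events, but only once found.
- Section 19.2 funds urinalysis at cycles 3 and 5. Section 4.0 has no such row, and a urinalysis is not a UPC. The timing matches the banked research urine of Section 14, whose collection ended with addendum 7, so the purpose of the line is unclear.

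**Step 3. Length of the gap**

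- Treatment: 365 / 28 = 13.04, so about 13 cycles with 0 scheduled UPC tests.
- Age of the only UPC at first dose: up to 14 days from test to registration, plus up to 14 days from registration to treatment (Section 6.5: "Treatment cannot begin prior to registration and must begin" within that limit), which gives 28 days.

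**Step 4. Patients who might be concerned**

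Section 15.17 lists proteinuria as common in renal cell carcinoma, at least 1% and below 10%. Assuming that band applies to the 39 planned patients:

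- Expected number: 39 × 0.01 = 0.39, to 39 × 0.10 = 3.9 (upper end excluded).
- Chance of at least one: 1 − 0.99^39 = 0.324 at 1%, and 1 − 0.90^39 = 0.984 as the rate nears 10%.

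These figures are for reported proteinuria of any grade. Patients reaching UPC 3 are a subset whose size the documents do not give. The band may also be low, since the note to Table 78 in Appendix VIII says laboratory findings were recorded as adverse events at the investigator's discretion.

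**Step 5. Effect of a scheduled test**

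Day 1 of cycles 3, 5, 7, 9, 11 and 13 falls on study days 57, 113, 169, 225, 281 and 337. That is 6 tests, 56 days apart. The longest on-treatment stretch without a scheduled UPC falls from up to 12 months to 8 weeks, apart from the 3-day visit window.

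**The case against.** The best defence is that discretionary testing is the written plan. Below UPC 3 the protocol leaves monitoring to clinical judgement, and the rule simply acts on a result when there is one, so Sections 4.0 and 8.3 do not contradict each other. Section 8.3 also has rules for thrombosis and bleeding without a dedicated scheduled test. Examination, weight, vital signs, creatinine, albumin and total protein are checked every cycle and may prompt a UPC. After a dose reduction, Section 7.12 asks for about 10 to 14 days of monitoring at each level. The number of patients who would reach UPC 3 is unknown and could be near zero.

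Part of this stands. No document sets a required UPC interval, the size figures are for a broader event than the one in the rule, and follow-up of a known high value is well covered until it falls below 3. The omission from Section 10.6 is weak evidence alone, because that list also leaves out platelets and QTc.

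The rest does not remove the gap. Thrombosis and bleeding usually declare themselves by symptoms, while heavy proteinuria often does not. None of the per-cycle checks is the measure in the rule, and Section 7.12 does not name UPC.

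**Conclusion.** The concern holds. Section 8.3 makes interruption, reduction and discontinuation depend on urine protein, and Section 4.0 schedules 1 UPC before registration and 0 afterwards, over as many as 13 cycles. This is a gap in detection; handling of a known event is specified.

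The count of scheduled tests rests only on the protocol. The patient numbers (about 0.4 to fewer than 4 of 39, any grade) assume that the Section 15.17 band carries over to this population. The number who would cross the threshold cannot be derived.

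The 12-month survival endpoint, sample size and power are untouched. The change should be made for patient safety and for a sound toxicity profile.

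**What to change.** Add on-treatment marks to the UPC row in Section 4.0, for example on Day 1 of every other cycle from cycle 3. The table already has an every-other-cycle column, which carries TSH and imaging (footnote 7: "Follow-up scans to be performed every other cycle (8 weeks"). The clinical team should confirm the interval. It should also consider a UPC after each restart, because under an 8-week schedule alone a recurrence could wait that long. In Section 19.2, state what the urinalysis at cycles 3 and 5 is for, then replace it with the scheduled UPC, add it to Section 4.0, or delete it.

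The cost is an amendment to one row and one budget line. No visits are added, since Section 7.3 already requires return "for evaluation at least every 28 days". Testing every other cycle needs up to 6 spot urines per patient, at most 6 × 39 = 234. Every cycle from cycle 2 would need up to 12 per patient, at most 12 × 39 = 468. Both totals fall if patients stop early, and any restart tests would be extra.

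Funding must be settled: the present UPC mark is not flagged as research funded, Section 19.2 names urinalysis and not UPC, and Section 19.1 charges routine care to patients. Earlier detection may also lead to more dose interruptions.

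### Section 8.3 proteinuria rule: the interrupt and restart conditions overlap when UPC and 24-hour protein disagree, and in one direction the continue row is met too

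*Combined protocol and SAP*

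**What the plan says.** The proteinuria block of Section 8.3 has two rows.

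- **Continue row.** The condition is UPC <3, with no mention of 24-hour protein. The action is "Continue pazopanib at the current dose; monitor as clinically indicated".
- **Interrupt row.** The condition is "UPC \geq 3 or 24-h urine protein \geq 3g". Step 1 interrupts. Step 2 asks for "Weekly UPC or 24-hr urine protein monitoring" and goes on "until UPC is <3 or 24-hr urine protein is <3 grams. Then restart pazopanib dose-reduced by 200 mg". Under Step 3, if the trigger "recurs, repeat steps 1 and 2". Under Step 4, if it "recurs and the pazopanib dose can no longer be reduced, discontinue pazopanib and continue follow-up per protocol".

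Section 8.11 lists a starting dose of 800 mg and two lower levels, 600 and 400 mg.

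Two other places bear on this. Section 3.16 puts the same two tests in order at entry: a UPC of 1 or more calls for a 24-hour collection, and then "Subjects must have a 24-hour urine protein value" below 1 g. The Section 4.0 schedule marks UPC only in the 14 days before registration and has no line for a 24-hour collection. Nothing says which test governs on treatment.

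**The concern.** A rule that stops treatment on either of two measurements, and releases it on either of the same two, can have its stop and release conditions true together. In logic, the opposite of (A or B) is (not A and not B); Step 2 uses (not A or not B). This is an observation about consistency and does not say what the clinical rule should be. The continue row adds a second overlap because it looks at UPC alone.

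At stake are patient safety and uniform dosing across the three Mayo sites. Two sites holding the same pair of results could act differently and each point to the table. A patient could also return to drug on the strength of one test while the test that prompted the interruption has not changed.

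**Working it through.** The plan gives no figure to reproduce. The check sets the three printed conditions side by side.

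Inputs, all from the proteinuria block of Section 8.3:

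- Continue: UPC <3.
- Interrupt: UPC ≥3 or 24-hour protein ≥3 g.
- Restart at 200 mg less: UPC <3 or 24-hour protein <3 g.

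| UPC | 24-hour protein (g) | Continue met | Interrupt met | Restart condition met | Conflict |
|---|---|---|---|---|---|
| <3 | <3 | yes | no | yes, but moot | no |
| <3 | ≥3 | yes | yes | yes | yes, all three |
| ≥3 | <3 | no | yes | yes | yes, interrupt and restart |
| ≥3 | ≥3 | no | yes | no | no |
| <3 | not done | yes | no | yes, but moot | no |
| ≥3 | not done | no | yes | no | no |
| not done | <3 | no | no | yes, but moot | no, though neither row applies |
| not done | ≥3 | no | yes | no | no |

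So interrupt and restart overlap in both discordant patterns. Continue joins them in only one, and that is because the continue row omits the 24-hour test, not because of the 'or' wording. With a single test used throughout there is no conflict.

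**Change of test.** Step 2 accepts either test each week. If a 24-hour value of 3.5 g triggers the interruption and the next weekly check is a UPC of 2.5, the restart condition is met with no evidence that the 24-hour value has moved.

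**Could the tests disagree near the cut-off?** Assume that 24-hour protein (g) is about UPC × daily creatinine excretion (g). The excretion values are assumptions; the documents give none. The UPC at which 24-hour protein equals 3 g is then 3 ÷ excretion.

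| Assumed excretion (g/day) | UPC at 24-hour protein = 3 g | UPC range where the tests disagree |
|---|---|---|
| 0.8 | 3 ÷ 0.8 = 3.75 | 3.0 to 3.75 (UPC ≥3, 24-hour <3 g) |
| 1.0 | 3 ÷ 1.0 = 3.0 | none |
| 1.2 | 3 ÷ 1.2 = 2.5 | 2.5 to 3.0 (UPC <3, 24-hour ≥3 g) |
| 1.5 | 3 ÷ 1.5 = 2.0 | 2.0 to 3.0 (same direction) |
| 1.8 | 3 ÷ 1.8 = 1.67 | 1.67 to 3.0 (same direction) |

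This shows that disagreement is possible in either direction, not how often it would occur in this trial.

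**How many patients?** Section 15.17 lists proteinuria as common in renal cell carcinoma (1% to below 10%). For the 39 patients to be accrued, 39 × 0.01 = 0.39 and 39 × 0.10 = 3.9. That range counts proteinuria of any grade. Those affected also need values near the cut-off and either two discordant tests or a change of test.

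**Comparison within Section 8.3.** Other rules there join the release measures by 'and'. LVEF recovery requires both a value at or above the lower limit of normal and a decrease of at most 10%. Blood pressure triggers on systolic or diastolic, but well-controlled (footnote e) requires both. Resumption after Grade 3 venous thrombosis requires all listed criteria. The proteinuria block has neither a matching release nor a governing test.

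**The case against.** The best defence is that Step 2 can be read as following one test until that same test falls below its limit: the monitoring phrase and the release phrase run in parallel, and one test used throughout gives no conflict. Section 4.0 schedules no 24-hour collection and no on-treatment UPC, and Section 8.3 asks for one test or the other, so a discordant pair arises only if a clinician orders both or changes test. Much of this stands and limits the size of the point. It does not remove it: the text does not say that the same test must be used, and it allows either each week.

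Three stronger readings are tempting, and the documents do not support them.

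- A reader might infer that any disagreement yields all three instructions. With UPC ≥3 and 24-hour protein <3 g the continue row does not apply.
- A reader might infer that the patient is told to stop and restart at the same moment. The steps are sequential; what overlaps is the conditions.
- A reader might infer that stable proteinuria must move a patient from 800 to 600 to 400 mg and then off treatment. Steps 3 and 4 apply when the finding recurs. A value that never fell has persisted, so that path needs a reading the text does not give.

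**Conclusion.** The point holds as a minor internal inconsistency. The interruption and restart conditions in the proteinuria block are not complementary, so if the tests disagree or the site changes test, a restart is permitted while the triggering value is unchanged. When UPC is <3 and 24-hour protein is ≥3 g, the table both continues and interrupts the same patient.

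The size is small. The 0.4 to 3.9 of 39 is a ceiling range for any proteinuria; the number meeting this conflict is lower and may be zero. It rests on the frequency band in Section 15.17 carrying over to this population. The discordance ranges rest on the assumed creatinine excretion.

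A reader might also infer that the trial's result is at risk. The primary endpoint is survival at 12 months from registration, and no endpoint definition, sample size or analysis depends on this rule.

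**What to change.** Reconcile the continue, interrupt and restart conditions in the proteinuria block of Section 8.3 so that no pair of results satisfies more than one of them. State which measurement governs when both are available or when they differ, as Section 3.16 does at entry, and say whether the test that triggered the interruption must also be the one that releases it. The continue row should also say what applies when only a 24-hour value is available. Which rule to adopt is the sponsor's decision.

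The cost is about one sentence in the Section 8.3 table. It need not add a test, and it changes nothing in the analysis.

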8.0 Dosage Modification Based on Adverse Events

8.1 Pazopanib

8.11 Pazopanib Dose Reduction Levels

Starting Dose	800 mg once daily
Dose Level -1	600 mg once daily
Dose Level -2	400 mg once daily

8.12

→ → Use the NCI Common Terminology Criteria for Adverse Events (CTCAE) version 4.0* unless otherwise specified ← ←			
CTCAE System/Organ/Class (SOC)	ADVERSE EVENT	AGENT	ACTION**
BASED ON INTERVAL ADVERSE EVENT			
Investigations	Platelet count decreased Grade 3 or 4	Pazopanib	Omit until ≤ 2 then restart at next lower dose level. If no recovery to grade 2, discontinue
Investigations	Electrocardiogram QT corrected interval prolonged ≥ 500 msec Grade 3	Pazopanib	Discontinue pazopanib
Renal and urinary disorders	Creatinine \geq Grade 3	Pazopanib	Omit until < 3 then restart at next lower dose level. If ≥ 3 recurs, reduce one dose level again until no dose can be given

→ → Use the NCI Common Terminology Criteria for Adverse Events (CTCAE) version 4.0* unless otherwise specified ← ←			
CTCAE System/Organ/Class (SOC)	ADVERSE EVENT	AGENT	ACTION**
Vascular disorders	Thromboembolic event DVT/PE Grade 3	Pazopanib	Omit and initiate anticoagulant. Restart at reduced dose if 
 • Subject must have been treated at desired level of anticoagulation for at least 1 week • No Grade 3 or 4 or clinically significant Grade 2, hemorrhagic events have occurred while on anticoagulation treatment. Note: When treating with warfarin, INR S/B monitored within 3 to 5 days after any change in pazopanib dosing and then at least weekly until INR is stable. The dose of warfarin may need to be adjusted to maintain the desired level of anticoagulation.
	Grade 4 Arterial Thrombosis/Ischemia Any Grade		Discontinue pazopanib Discontinue pazopanib
Vascular disorders	Hypertension	Pazopanib	See table 8.2
Gastrointestinal disorders	Any GI bleed Grade 2-4	Pazopanib	Discontinue pazopanib
Respiratory, thoracic and mediastinal disorders	Any Pulmonary bleed Grade 2-4	Pazopanib	Discontinue pazopanib
Dermatology/ Skin	Dermatitis Grade 2 skin changes w/pain, limiting ADL's Grade3 severe skin changes w/pain Limiting self care ADL's	Pazopanib	Omit until ≤ 1 , then restart at next lower dose level. If recurrent, reduce by another dose level or discontinue Discontinue

→ → Use the NCI Common Terminology Criteria for Adverse Events (CTCAE) version 4.0* unless otherwise specified ← ←			
CTCAE System/Organ/Class (SOC)	ADVERSE EVENT	AGENT	ACTION**

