All Other	Grade 2 or 3, if clinically significant Grade 4	Pazopanib	Omit until ≤ 1 Discontinue Pazopanib

* Located at

http://ctep.cancer.gov/protocolDevelopment/electronic_applications.ctc.htm

** Use the following to describe actions in the Action column:

- Omit = Treatment is not given for this cycle
- Hold/Delay = Treatment can be made up as part of this cycle
- Discontinue = Treatment is totally stopped

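### The bleeding rules in 8.12, 8.2 and 8.3 conflict for Grade 2 hemorrhoidal bleeding and, read literally, for Grade 3 bleeding outside the gut and lung, and nothing says which table governs

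*Combined protocol and SAP*

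**What the plan says.** Three tables carry bleeding rules. The table under 8.12 covers adverse events in the interval between visits, 8.2 covers the time of retreatment, and 8.3 gives algorithms by type of event without limiting them to either time.

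- **8.12 and 8.2, bleeding rows.** Each has two, "Any GI bleed Grade 2-4" and "Any Pulmonary bleed Grade 2-4". The action in both is to discontinue.
- **8.12 and 8.2, All Other row.** The grade cell in 8.12 reads "Grade 2 or 3, if clinically significant Grade 4" and the action cell "Omit until ≤ 1 Discontinue Pazopanib". Each cell holds two entries run together: clinically significant Grade 2 or 3 is omitted until Grade 1 or less, and Grade 4 is discontinued. 8.2 is the same, with hold in place of omit.
- **Definitions under the tables.** "Omit = Treatment is not given for this cycle" and "Discontinue = Treatment is totally stopped", so the first is a pause and the second is permanent.
- **8.3, Hemorrhage/Bleeding, Grade 2.** "If pulmonary or GI bleed (other than hemorrhoidal bleeding), discontinue pazopanib and continue follow-up per protocol". Any other Grade 2 bleed is interrupted until Grade 1 or less and then restarted, with a dose reduction to be considered.
- **8.3, Grade 3 or 4, or recurrent Grade 2 or worse after interruption or reduction.** "Discontinue pazopanib and continue with follow-up per protocol". No site is named, so the rule applies to all sites.

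**The concern.** An investigator facing a bleed can open any of the three tables. If they disagree, two of the three Mayo sites could handle the same event in opposite ways while each follows the written protocol. The disagreement runs in both directions. For a hemorrhoidal bleed, 8.12 and 8.2 end treatment permanently where 8.3 allows it to resume. For a Grade 3 bleed such as hematuria or epistaxis, a literal reading of 8.12 and 8.2 lets treatment resume where 8.3 ends it. Bleeding is a risk that the protocol itself singles out: Section 15.26 asks nurses to watch for it because of the drug's similarity to other VEGF inhibitors, and Section 1.5 promises clear management guidance for such class effects.

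**Working it through.** There is no plan figure to reproduce; the check is a row-by-row comparison.

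| Event | 8.12 | 8.2 | 8.3 | Result |
|---|---|---|---|---|
| Grade 2 GI (not hemorrhoidal) or pulmonary | stop | stop | stop | agree |
| Grade 2 hemorrhoidal | stop | stop | interrupt, then restart | **conflict** |
| Grade 3 or 4 GI or pulmonary | stop | stop | stop | agree |
| Grade 2 other site, first event, clinically significant | omit (All Other) | hold (All Other) | interrupt, then restart | all pause |
| Recurrent Grade 2, other site | no recurrence rule | no recurrence rule | stop | **8.12 and 8.2 silent** |
| Grade 3 other site, clinically significant | omit (All Other) | hold (All Other) | stop | **conflict through catch-all** |
| Grade 4 other site | stop | stop | stop | agree |

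**Does a hemorrhoidal bleed fall in the GI row?** 8.3 has to carve it out of the GI bleeds to exempt it, so the protocol treats it as one of them. The GI row in 8.12 and 8.2 covers every GI bleed of Grade 2 to 4, so it is included there.

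**Does an other-site Grade 3 bleed fall under All Other?** 8.12 and 8.2 have no other row that would take it. Read literally, a clinically significant one does.

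**Does a cross-reference settle it?** Only the hypertension rows carry one: 8.12 points to 8.2, and 8.2 points to 8.3. The bleeding rows point nowhere, and the protocol contains no statement of precedence.

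**Does Section 7.4 settle it?** It ends treatment when a Grade 3 or 4 toxicity forces a break and treatment cannot be restarted after a delay of 28 days or more. It does not say whether a Grade 3 bleed that resolves sooner may be followed by more treatment.

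**Size.** The nearest figures are in Table 78 (Appendix VIII), which lists hematuria and epistaxis as Common in RCC. Section 15.17 defines Common as at least 1% and below 10%. With 39 patients:

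- lower end: 0.01 × 39 = 0.39
- upper end: 0.10 × 39 = 3.9

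So each term would be expected in about 0.4 to 4 patients at any grade. This does not measure the conflict, which concerns only Grade 3 and recurrent Grade 2 events at such sites, plus Grade 2 hemorrhoidal bleeds. The documents give no rate for any of these.

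**The case against.** The best defense is that a specific rule overrides a general one. All Other is a residual row, and 8.3 has a dedicated bleeding block. 8.3 also has its own catch-all for other clinically significant events, with the same split between Grade 2 or 3 and Grade 4, and it keeps bleeding out of that catch-all. Falling LVEF and proteinuria likewise have no row in 8.12 or 8.2 and are handled in 8.3, and liver toxicity is handled in 8.4. The natural reading is then that All Other covers only events without an algorithm of their own, and the Grade 3 conflict disappears.

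This has force: the Grade 3 conflict is less certain than the hemorrhoidal one, and the recurrence point, which depends on the same reading, is silence more than contradiction. For GI and pulmonary bleeds, 8.12 and 8.2 mostly need no recurrence rule, because the first Grade 2 event already stops treatment. But the protocol nowhere states the reading. The defense also leaves the hemorrhoidal conflict untouched, because there both rules are specific.

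A reader might go on to infer that the two conflicts are equally firm, that up to 4 patients in 39 would be affected, or that 8.3 is the correct rule and the other tables are unsafe. The documents support none of these. The first overlooks the catch-all. The second takes an all-grade figure for one term as a count of conflicting cases. The third is a clinical judgment that the text does not make.

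**Conclusion.** The tables contradict each other, and no order of precedence is given. The conflict on Grade 2 hemorrhoidal bleeding is direct. The conflict on Grade 3 bleeding outside the gut and lung holds on a literal reading, for clinically significant events, and rests on the assumption that the catch-all row in 8.12 and 8.2 does not yield to 8.3. Recurrent Grade 2 or worse bleeding is a stop in 8.3, with no matching provision for other sites in 8.12 or 8.2.

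The number of patients affected cannot be computed and is likely small, though each case is a choice between a pause and a permanent stop. A reader might also infer damage to the main result. The documents do not support that: Sections 16.11 and 16.311 count 12-month survival from registration in all eligible patients who began treatment, and Section 13.3 sends patients who stop for reasons other than progression to event monitoring. Neither the analysis set nor the endpoint definition depends on which table was followed.

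**What to change.** Reconcile the bleeding rules in 8.12, 8.2 and 8.3 so that all three give the same action for each combination of site, grade and recurrence, with hemorrhoidal bleeding and sites outside the gut and lung addressed explicitly. Alternatively, state in Section 8 which table governs bleeding. The sponsor's clinical lead decides which action stands; this review takes no position on that.

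The cost is a wording amendment to the bleeding rows of these tables, with no added procedures.
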